1. A member of the study team (usually the research assistant (RA)) will determine initial eligibility by checking the patient's chart/ED board for their BP. The RA will ask patients with BP $\geq 130/80$ mmHg if they have a history of HTN. If yes, the RA will ask the patient: 1) If they have an existing relationship (such as family member) with a 14-24-year-old, and 2) If the youth has access to internet or a data plan, as well as a smart phone or computer (to complete the digital badge intervention).
2. If the patient is eligible and interested in participating in the study, the RA will discuss the study with the patient, answer questions, and obtain written consent.
3. The RA will then collect the patient's BP using the study BP cuff (which is then used for patient follow-up visits so that there is no variation in BP instrument measurements) and follows the BP measurement protocol. Adult completes baseline assessments including hypertension knowledge.
4. The RA will give the patient a study flyer to bring home to the potential youth participant and will collect the patient's contact information. The patient will be asked to share the information with the youth and call the study team if both adult and youth are interested in participating. If the adult is willing to provide the youth's contact information, we will collect it.
5. If the team does not hear from the patient after 3 days, they will contact (call, email, and/or text) the patient to follow-up about participation. If we have the youth's contact information from the adult, we will contact the youth directly and tell them that we received their information from the adult (see youth recruitment script). The adult patient and youth must both agree to participate in the study for the dyad to participate.
6. After a member of the study team discusses the study with the youth (and parent or legal guardian if youth is 14-17), answers questions, and obtains written consent (including parental/legal guardian consent if youth is 14-17 years old).
7. Youth completes baseline assessments including hypertension knowledge and self-efficacy scales.
8. Each dyad will be randomized into one of two arms- either intervention or control arm:

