4.3 Number of Subjects

A. Total Number of Subjects

Aim 1: Participants for the design sessions will be 10-15 adults in total and 10-15 youth in total. Each design session will be a focus group of approximately 5-8 people or one-on-one interview and we anticipate 2 design sessions for each group (adults and youth). One adult session will be in Spanish to be inclusive of participants with limited English proficiency.

Aim 1a: 15 participants

Aim 2: 100 participant dyads (1 youth + 1 adult = 1 dyad), 200 total

Aim 3: 10 adults and 10 youth will be recruited for phone interviews. In the first cohort, all members of the intervention group and in the school cohort all participants will complete questionnaires. () .

B. Total Number of Subjects If Multicenter Study

Not applicable

C. Feasibility

In the US, 33% of individuals have HTN⁶ and for adults with HTN, BP control decreased from 54% in 2013-2014 to 44% in 2017-2018.⁷ BP is elevated at almost half (44%) of all ED visits- compared to 27% of primary care doctor visits.⁸ Data demonstrates that ED patients' elevated BP is from HTN, and not a result of pain or anxiety from the ED visit.^{9,10} From 2006 to 2012, HTN-related ED visits made up 24% of all ED visits, and rose 5% per year.¹¹

Based on the high prevalence of uncontrolled HTN in the US, and especially in ED patients compared to patients in other settings, we anticipate that it will be feasible to recruit our study sample size of 100 patients for Aim 2 given we are recruiting from a large ED of 70,000 patients. (Aim 1 sample size of 20-30 participants is also feasible given the prevalence of HTN in the community.)

For the school cohort, there are about 200 students at the school, so we anticipate that recruiting enough students for the study will be feasible, especially because all study procedures will take place at school or at home.

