4.4 Consent Procedures

A. Consent Process

▪ **Location of Consent Process**

Aim 1: Participants will receive an information letter about the study, and their consent to participate will be their participation in the discussion. Parental permission will take place electronically through RedCap for participants 15-17 years old, and will be required in order for 15-17 year olds to participate.

Aim 1a: Participants will receive an information letter about the study, and their consent to participate will be their participation in the discussion. Parental permission will take place electronically through RedCap for participants 15-17 years old, and will be required in order for 15-17 year olds to participate.

Aim 2: For first cohort: Adult consent by the ED patient will take place in the ED through RedCap so that the study team can collect their baseline BP and other characteristics at baseline. Assent and parental permission for youth participants will take place electronically through RedCap. A member of the study team will walk the youth participant and their parent/legal guardian through the study and appropriate form via phone or Zoom.

School cohort: Adult and youth consents and parental permission forms will be completed electronically through Redcap. A member of the study team will describe the study, answer questions about the study, and will consent the participant in person or on Zoom while the participant signs the form on Redcap.

Aim 3: Interview: Participants will receive an information letter about the study, and their consent to participate will be their beginning the interview. Parental permission will take place electronically through RedCap for participants 14-17 years old, and will be required in order for 14-17 year olds to participate.

For the school cohort: The interview will be included in the consent form for the rest of the study.

- **Ongoing Consent**

Not applicable

- **Individual Roles for Researchers Involved in Consent**

Participants will be consented by the PI ([name]) and research assistants. (

- **Consent Discussion Duration**

It is expected that the consent/assent/parental permission process (for each Aims) will take approximately 5 minutes each.

- **Coercion or Undue Influence**

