6.0 Data Management Plan

6.1 Data Analysis

Aim 1: *Quantitative*: Questionnaire data will be analyzed descriptively. *Qualitative*: Audio recordings will be transcribed verbatim, and will be analyzed using Gale's Framework Method.⁴² As such, three members of the study team will conduct open coding for all transcripts and will meet to agree on a working analytical framework. Categories will be grouped into subsequent themes as related to the digital badge. The PI will then refine the digital badge based on findings from the design sessions with input from mentors.

Aim 1a: Qualitative data will be collected from youth on their feedback on the hypertension knowledge assessment tool. In addition, we will analyze item discrimination and internal reliability of the tool based on their completion of the tool in its entirety. Data from a brief demographic survey will be analyzed descriptively.

Aim 2: Descriptive statistics will be used to assess participant characteristics and covariate balance across study arms. To determine balancing of important measures that may influence outcome variables, the analysis will implement t-tests for continuous variables and chi-square tests for categorical variables. STATA will be used to carry out all statistical analysis. Analysis will include mean BP change from baseline to 2-month follow-up for each arm using a t-test. Multivariate linear regression analysis will also be used to compare the two groups, including a dummy variable for group, baseline BP, and any covariates found to be unbalanced across arms. For youth empowerment, pre- and post-intervention data will be compared with significance testing via t-test.

Aim 3: *Quantitative:* Quantitative data will be analyzed descriptively. *Qualitative:* Interviews will be analyzed using Gale's Framework Method⁴² (see Aim 1 for more details).

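### Extra covariates in the blood pressure regression are chosen by balance tests between randomised arms; two or three prognostic ones fixed in advance would be a cheap improvement

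*Combined protocol and SAP*

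**What the plan says.** Section 6.1 (Data Analysis, Aim 2) plans two BP comparisons for the randomised emergency department (ED) cohort.

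- A t-test: "Analysis will include mean BP change from baseline to 2-month follow-up for each arm using a t-test".
- A regression: "Multivariate linear regression analysis will also be used to compare the two groups". The terms of that model are described as "including a dummy variable for group, baseline BP, and any covariates found to be unbalanced across arms".

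The screening step comes just before these. Its purpose is stated as "To determine balancing of important measures that may influence outcome variables", and for this "the analysis will implement t-tests for continuous variables and chi-square tests for categorical variables".

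Group and baseline BP are therefore always in the regression. Any other covariate enters only if it is found unbalanced. Section 6.1 does not list the candidates, give a threshold for imbalance, or say which of the two BP analyses is primary. No other section names a fixed covariate set.

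**The concern.** Dyads are randomised, with one adult in each, so a baseline difference between the arms as randomised arises by chance. A covariate sharpens the BP comparison because it predicts follow-up BP, not because its p-value between arms happens to be small. The plan limits the pool to measures thought to matter for outcome, which is sensible, but within that pool entry depends on imbalance alone. A strong predictor that happens to be balanced is left out, although adjusting for it would cut residual variance.

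Two things are at stake. One is the precision that a fixed prognostic set could add. The other is transparency: with candidates and threshold unstated, nobody can say beforehand which adjusted estimate will be reported. Validity is not at stake, because the selection uses baseline data by arm and not outcomes.

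**Working it through.** **No figure to reproduce.** Section 1.5 defers the sample size calculation to later studies. The documents give no alpha, SD, effect size, correlation, balance threshold or allocation ratio.

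**Input from the documents.** Section 4.3 gives "100 participant dyads (1 youth + 1 adult = 1 dyad), 200 total". These are not split between the ED and school cohorts, and only the ED cohort is randomised and has BP as an outcome. So 50 per arm is the most the target allows under equal allocation; 40 and 25 per arm were also run.

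**Assumptions.** Two-sided 5% tests, 1:1 allocation, independent candidates, balance threshold p<0.05, 10 candidates of which 3 are prognostic, baseline-to-follow-up correlation 0.4, effect 0.5 SD, and covariate-outcome correlation r of 0.1, 0.2 or 0.3.

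**Step 1: how often chance picks the model.** With K independent candidates, the probability that at least one enters is 1 − 0.95^K.

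- K = 5: 1 − 0.95^5 = 0.226
- K = 10: 1 − 0.95^10 = 0.401
- K = 15: 1 − 0.95^15 = 0.537
- K = 10 at p<0.10: 1 − 0.90^10 = 0.651

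Each prognostic covariate enters with probability 0.05 (4.7–5.2% in simulation). With three of them, none enters with probability 0.95^3 = 0.857.

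**Step 2: power by simulation at 50 per arm (6,000 trials per cell).**

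| Model | r = 0.1 | r = 0.2 | r = 0.3 |
|---|---|---|---|
| Baseline BP only | 76.8% | 76.6% | 76.2% |
| Plan's rule | 75.9% | 76.0% | 76.6% |
| Three fixed, all prognostic | 77.1% | 81.4% | 89.3% |
| Three fixed, one prognostic | 75.5% | 77.5% | 79.9% |
| Three fixed, none prognostic | 75.2% | 75.7% | 75.0% |

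Fixed set minus rule, for r = 0.1 / 0.2 / 0.3:

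- all three prognostic: +1.2 / +5.4 / +12.7 points
- one prognostic: −0.4 / +1.5 / +3.3 points
- none prognostic: −0.7 / −0.3 / −1.6 points

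Type I error of the rule was 5.2 / 4.8 / 4.0%.

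**Step 3: check by formula.** With n per arm, N = 2n and q covariates, the variance of the adjusted difference is s² × (2/n) × [1 + q/(N − q − 3)], where s² is the residual variance and the last factor is the price of adjustment.

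- Baseline BP only (q = 1): s² = 1 − 0.4² = 0.84; SE = √(0.84 × 0.04 × 1.0104) = 0.184; 0.5/0.184 = 2.71; power 76.6%.
- Three fixed, r = 0.2 (q = 4): s² = 0.84 − 3 × 0.04 = 0.72; SE = √(0.72 × 0.04 × 1.043) = 0.173; ratio 2.89; power 81.5%.
- Three fixed, r = 0.3 (q = 4): s² = 0.84 − 3 × 0.09 = 0.57; SE = √(0.57 × 0.04 × 1.043) = 0.154; ratio 3.24; power 89.4%.

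These agree with the simulation.

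**Step 4: smaller samples, rule against three fixed prognostic covariates (r = 0.1 / 0.2 / 0.3).**

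- 40 per arm: 66.1 / 66.0 / 66.4% against 67.5 / 71.5 / 81.8%
- 25 per arm: 44.8 / 44.9 / 44.3% against 46.3 / 49.7 / 59.6%

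**Step 5: a second set of assumptions.** With SD 18 mmHg, baseline correlation 0.5, a true difference of 8 mmHg, 8 candidates, and three prognostic ones jointly explaining 10 / 20 / 30% of outcome variance, power at 50 per arm was 71 / 72 / 72% under the rule and 76 / 83 / 90% with the three fixed. Baseline BP alone gave 71–72%.

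**The case against.** The strongest reply is that this is a refinement and not a fault. Baseline BP, probably the best single predictor, is always in the model. An unadjusted t-test with no selection is also planned. The study is a pilot with no power target, and the rule neither biases the comparison nor raises type I error. All of that stands, and it limits the weight.

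The upper end of the gain is also demanding. At r = 0.3 three covariates explain 3 × 0.09 = 27% of outcome variance, against 0.4² = 16% for baseline BP. Nothing in the documents shows that the available covariates predict follow-up BP so well, so +13 points is an upper bound and not an expectation. At the low end the differences are close to simulation error, about √(0.76 × 0.24/6000) = 0.55 points per cell. At 25 per arm and r = 0.1 the formula in Step 3 gives 45.1% for the fixed set and 46.4% for baseline BP alone, so weak covariates bring no gain there.

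Two points of wording are fair. The 5% entry rate presumes a strict p-value threshold, which Section 6.1 implies but does not state. And imbalance is pure chance only among all randomised adults: if the tests were run on those who return at 2 months, dropout could contribute. Section 6.1 does not say which set is tested.

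None of this defends the selection rule. It gains essentially nothing over baseline BP alone and leaves the model open until arm-labelled data are seen.

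**Conclusion.** The concern holds, as an improvement of modest weight that should be made. Against the plan's rule at 50 per arm, a fixed set of three changes power by about +1 to +13 points if all are prognostic, 0 to +3 if one is, and −2 to 0 if none is. With all three prognostic the gain is +1 to +15 points at 40 per arm and +2 to +15 at 25. The sizes rest on assumed correlations, effect and threshold. The direction does not depend on the exact values: the rule matched baseline BP alone under both sets of assumptions. The gain in transparency does not depend on them at all.

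**What to change.** In Section 6.1, stop using balance tests to select covariates, and show baseline characteristics by arm without p-values. Before anyone examines arm-labelled data, fix the BP model as arm, the baseline value of the outcome, and two or three covariates chosen on clinical grounds as likely predictors of follow-up BP, kept whatever balance is seen. The list should stay short because the number of randomised dyads is uncertain.

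Use only variables measured before randomisation:

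- **Hypertension knowledge.** Section 1.3, step 3, says "Adult completes baseline assessments including hypertension knowledge", ahead of randomisation at step 8. Section 1.9 (Timing and Frequency) places this assessment at the start of the intervention, so the two must be reconciled first.
- **Age and language.** Both are screened under Section 4.1 C; confirm that they are recorded as values and not only checked as eligibility limits.
- **Other items.** Section 4.4 says adult consent is taken in the ED "so that the study team can collect their baseline BP and other characteristics at baseline" but does not list the characteristics. The team should confirm what is held.

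The cost is one paragraph, two or three degrees of freedom, and no new data if the covariates are already recorded. The risk is a loss of up to about 2 points of power if those chosen turn out not to be prognostic.

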6.2 Data Security

The PI is responsible for protecting the confidentiality of subjects' data. All participant data will either be de-identified or will use a coded list of identifiers prior to analysis (will remove identifiers prior to analysis). list of identifiers will be destroyed at the end of the study.

All data will be entered into electronic database (RedCap). RedCap is a secure, web-based application. There will be no paper charts/data entry. This will minimize the potential for loss of information and breech of privacy. Patient confidentiality will be maintained through secured, password protection computerized data collection. All documents and information about this study will be kept confidential in accordance with federal, state, and local laws and regulations. The results of this study will be published. If results are published, no subject will be identified by name.

6.3 Data and Safety Monitoring

Not applicable

6.4 Reporting Results

A. Individual Subjects' Results

Not applicable

B. Aggregate Results

Not applicable

C. Professional Reporting

Study methods and findings will be submitted as peer-reviewed abstracts to national conferences and manuscripts to professional journals.

D. Clinical Trials Registration, Results Reporting and Consent Posting

This research qualifies as a clinical trial and will be registered in clinicaltrials.gov.

6.5 Secondary Use of the Data

Not applicable

7.0 Research Repositories – Specimens and/or Data

Not applicable

8.0 Approvals/Authorizations

RUG form has been uploaded.

The cooperation letter from the school has also been uploaded.

